10.10 Age

The age at consent will be determined as follows:

- If age is recorded in the eCRF then this will be the one used for analysis
- If only year of birth is known, Date of Birth is imputed to the 15 June of the year of birth and age is derived as:

$$\text{Age at Informed Consent (years)} = (\text{Date of Informed Consent} - \text{Date of Birth} + 1) / 365.25$$

However, if derived age is resolved to 17-year-old and inclusion criteria 6.1.1 is met then age will be set to 18 years.

Based on the above age will also be categorized as ≤ 18 , > 18 to ≤ 45 , > 45 to ≤ 65 and > 65 years old and labelled ≤ 18 , > 18 to ≤ 45 , ≥ 46 to ≤ 65 and > 65 years, respectively.

10.11 Body Mass Index

At each weight measurement, the Body Mass Index (BMI) will be derived using height collected at screening.

It is calculated using the following formula:

$$\text{BMI (kg/m}^2\text{)} = \text{Weight (kg)} / [\text{Height (cm)}] \times 0.01]^2$$

Based on the above value BMI will also be categorized as follows:

- < 18.5 as underweight;
- ≥ 18.5 and < 25.0 as normal or healthy weight;
- ≥ 25.0 and < 30.0 as overweight;
- ≥ 30.0 as obese.

10.12 Disease History

As part of Disease history description, the following parameters will be derived:

- **Time since diagnosis of MS (years)**
 $(\text{Date of Informed consent} - \text{Date of MS diagnosis} + 1) / 365.25;$
- **Age at diagnosis of MS (years)**
 $(\text{year of MS diagnosis} - \text{year of Birth} + 1)$
- **Time since onset of spasticity due to MS (years)**
 $(\text{Date of Informed consent} - \text{Date of onset of spasticity due to MS} + 1) / 365.25;$
- **Age at onset of spasticity due to MS (years)**
 $(\text{year of onset of spasticity due to MS} - \text{year of Birth} + 1);$
- **Time between MS diagnosis and onset of spasticity due to MS (years)**
 $(\text{Date of onset of spasticity due to MS} - \text{Date of MS diagnosis} + 1) / 365.25;$
- **Time between MS diagnosis and onset of spasticity due to MS (months)**
 $(\text{Date of onset of spasticity due to MS} - \text{Date of MS diagnosis} + 1) / 30.4375.$

The following conversion will be applied as appropriate:

- Time since last relapse (months) = Time since last relapse (years) * 12,
- Time since last relapse (months) = Time since last relapse (days) / 30.4375.

Age at diagnosis of MS and age at onset of spasticity due to MS are only using year because only year of birth is planned to be collected.

If date of MS diagnosis and/or date of onset of spasticity due to MS are unknown or partial, they will be imputed as follow:

- if only day is missing, it will be imputed to the 15th of the month,
- If day and month are missing, they will be imputed to the 30 June of the year,
- However, if any of these dates fall after the informed consent date, they will be set to the informed consent date. If the date of onset of spasticity due to MS before the date of MS diagnosis due to imputation rule, it will be set to the date of MS diagnosis.

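### Age at MS diagnosis and age at onset of spasticity add a whole year to the calendar-year difference, so both baseline rows are about one year too high

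*SAP*

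**What the plan says.** SAP 10.12 (Disease History) defines two ages, both labelled in years:

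- age at diagnosis of MS = year of diagnosis − year of birth + 1;
- age at onset of spasticity = year of onset − year of birth + 1.

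It gives a reason for working in whole years: "Age at diagnosis of MS and age at onset of spasticity due to MS are only using year because only year of birth" (nothing finer will be recorded, according to the rest of that sentence). It gives none for the added 1.

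The other derivations in the same section (time since diagnosis, time since onset, time between the two) take a difference of dates, add 1 and divide by 365.25 or 30.4375. There the 1 is a day.

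Age at consent is defined in SAP 10.10. The first rule is "If age is recorded in the eCRF then this will be the one used for analysis". The fallback is "If only year of birth is known, Date of Birth is imputed to the 15 June of the year of birth". The calculation is then consent date minus birth date plus one day, divided by 365.25.

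Both disease ages are reported with the disease characteristics in SAP 12.2.5, which refers back to 10.12.

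**The concern.** Adding 1 to a difference of dates is the usual convention for counting days inclusively. Carried into a formula whose unit is years, it adds a year. On this rule an event in the year of birth would be given age 1.

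Having only the year of birth justifies taking a difference of calendar years. It does not justify adding to it: the plain difference is already centred on the exact age.

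What is at stake is the description of the trial population. Two baseline rows would be shifted in the same direction for essentially every patient. They would also fail to reconcile with age at consent and time since diagnosis, which are reported in the same set of baseline summaries.

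**Working it through.** The documents give no numerical result for these ages, so there is no figure to reproduce. The check applies the SAP formulas as written.

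**Error against exact age.** Let D be the difference in calendar years, u the position of the event within its year and v the position of the birth within its year (both from 0 to 1).

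- Exact age = D + u − v.
- SAP age = D + 1.
- Error = 1 − u + v, which lies between 0 and +2 whatever the dates.

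If u and v are independent and uniform (an assumption; the documents give no distribution), the mean error is 1 − 0.5 + 0.5 = +1.0 year. A simulation of 200,000 patients gave a mean of +1.00 and a range of 0.00 to 2.00.

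**Error against completed years.** Completed age is D if the birthday has passed by the event date, and D − 1 otherwise. The SAP value D + 1 is therefore high by exactly 1 or exactly 2 years. Under uniform dates each occurs about half the time, so the mean is +1.5 (simulation: 1.50).

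**Consistency with age at consent, 15 June birth date.** In age at consent minus time since diagnosis, the consent date and the two added days cancel. What remains is (diagnosis date − 15 June of birth year)/365.25, or about D + u − 0.45. The SAP age exceeds this by 1.45 − u:

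- between +0.45 and +1.45 for every patient, mean +0.95;
- +0.96 for every patient whose diagnosis date is imputed to 30 June under SAP 10.12.

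**Worked example.** Birth year 1980, diagnosis 30 June 2010, consent 10 January 2022:

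- age at consent = 15,185/365.25 = 41.57;
- time since diagnosis = 11.53;
- difference = 30.04;
- SAP age at diagnosis = 2010 − 1980 + 1 = 31.

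**An impossible record.** Birth year 1980, diagnosis 5 January 2021, consent 10 January 2022. With screening on the consent date, this meets the 12-month diagnosis requirement of Protocol 6.1.4. The SAP gives age at diagnosis 2021 − 1980 + 1 = 42, but age at consent 41.57: the patient is older at diagnosis than a year later.

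**Consistency with age at consent, whole-year eCRF age.** SAP age at diagnosis minus (eCRF age − time since diagnosis) averaged +1.5 years in simulation, with a range of about 0 to +3.

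**With the added 1 removed.** The error against exact age becomes v − u: mean 0.00, range about −1 to +1. Against completed years the mean is +0.5. With a 15 June birth date and a 30 June diagnosis date, the plain year difference agrees with age at consent minus duration to within 15/365.25 = 0.04 year.

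**The case against.** The arithmetic is hard to dispute; the case on the other side is about importance and precision.

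- **Descriptive only.** Neither age is a model covariate (SAP 9.2), a subgroup variable (SAP Tables 12.1-1, 12.5-2 and 12.7-1), an eligibility criterion or a major protocol deviation. The age subgroups use age at consent, which carries no extra year. The durations are unaffected, the shift applies to both sequences alike, and it cancels in the difference between the two ages. Protocol 13.5.2 plans no formal comparison of baseline data. All of this stands and sets the ceiling on severity. Only two rows are wrong, not the whole disease table.
- **The eCRF age takes precedence.** If it is recorded in whole years, the rows would not reconcile exactly even after correction: removing the 1 leaves a discrepancy averaging +0.5 year, from about −1 to +2. A single record may also agree by chance under the present rule. This stands, so certain disagreement for every patient holds only for the 15 June route. With an eCRF age the summary rows still differ by about 1.5 years on average, of which a full year comes from the added 1.
- **The averages rest on uniform dates.** True, but the direction and the limits do not.

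**Conclusion.** The concern holds. The two formulas are wrong as written, and nothing elsewhere in the SAP corrects them. The reported ages are never too low. Against exact age they are too high by 0 to 2 years, on average 1.0; against completed years by 1 or 2 years, on average 1.5. The averages assume birth and event dates spread independently and evenly over the calendar year. The consequence is minor: two baseline rows are biased and inconsistent with their neighbours, and no efficacy or safety conclusion changes.

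**What to change.** Either of two changes to SAP 10.12 removes the bias against exact age:

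1. delete the added 1 from both age formulas; or
2. use the SAP 10.10 birth date for both: (event date − 15 June of birth year + 1 day)/365.25, with the event date imputed as 10.12 already provides.

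The second matches the fallback definition of age at consent and uses the month and day of the event where known. The first is simpler, but the SAP should then say that the result approximates decimal age, because it averages half a year above age in completed years.

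Before choosing, reconcile the source data: Protocol 9.2.3 lists date of birth among the items obtained at screening, whereas SAP 10.12 says only the year is planned. If full birth dates are held, exact ages can be calculated directly.

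The cost is two formulas and their programming, with no effect on any other analysis.

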10.13 Renal Function Formula

Estimated Glomerular filtration rate (eGFR)

For the purpose of summary, the eGFR collected by central laboratory will be used.

eGFR will also be categorized as follows:

- ≥ 90 as normal,
- ≥ 60 and < 90 as mild reduction,
- ≥ 30 and < 60 as moderate reduction,
- ≥ 15 and < 30 as severe reduction,
- < 15 as end stage kidney failure.

10.14 Prior and Concomitant Medication Start/Stop Date Imputation Rule

Table 10.14-1 Imputation Rules for Partial Medication Dates (D = day, M = month, Y = year)

Parameter	Missing	Additional Conditions	Imputation
Start date for concomitant meds	D only	M and Y same as M and Y of first dose of study drug	Date of first dose of study drug
		M and/or Y not same as date of first dose of study drug	First day of month but should fall on or after first study drug intake or if impossible after informed consent date
	M and D	Y same as Y of first dose of study drug intake during Period 1 and 2	Date of first dose of study drug
		Y after Y of first dose of study intake during period 1 but same Y as 1 st study drug intake during Period 2	Date of first drug intake during period 2
		Y after Y of last study drug intake	The earliest date between date of last study drug intake and end of study date
	M, D, and Y	Not allowed by the system	Not applicable
Stop date for concomitant meds	D only	M and Y same as M and Y of last dose of study drug	The earliest date between date of last dose of study drug and end of study date
		M and/or Y not same as date of last dose of study drug	The earliest date between last day of month and end of study date
	M and D	Not allowed by the system	Not applicable
	M, D, and Y	Not allowed by the system	Not applicable

Meds = Medications.

Note: In all cases, if an estimated start date is after a complete stop date, use the first day of the stop date month.

Similarly, if the estimated stop date is before a complete or imputed start date, use the last day of the start date month.

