6.1 Inclusion Criteria

Screening (Visit 1)

For inclusion in the trial, patients must fulfill ALL of the following criteria:

- 6.1.1 Male or female, aged 18 years or above.
- 6.1.2 Willing and able to give informed consent for participation in the trial (see [Section 15.2](#)).
- 6.1.3 Willing and able (in the investigator's opinion) to comply with all trial requirements.
- 6.1.4 Has had a diagnosis with any disease subtype of MS, by revised 2017 McDonald criteria, for at least 12 months prior to Visit 1 and is expected to remain stable for the duration of the trial.
- 6.1.5 Has an MAS untransformed score of at least 2 in 2 or more of 6 muscle groups (right knee flexors, left knee flexors, right knee extensors, left knee extensors, right plantar flexors, or left plantar flexors) at Visit 1.
- 6.1.6 Currently receiving optimized treatment with at least 1 oral antispasticity drug (baclofen, tizanidine, and/or dantrolene) that has been stable for at least 30 days prior to Visit 1. Despite optimization, the patient does not have adequate relief of spasticity symptoms, including muscle spasms. Optimization of antispasticity medications is defined as having reached the most efficacious and best tolerated dose according to the relevant local prescribing information. The patient must be willing to maintain the same antispasticity medication and not plan to initiate a new course of physiotherapy for the duration of the trial.
- 6.1.7 If currently receiving an approved MS disease-modifying therapy, it must be at a stable dose for at least 3 months prior to Visit 1 and is expected to remain stable for the duration of the trial.

- 6.1.8 If currently receiving dalfampridine or fampridine, it must be at a stable dose for at least 3 months prior to Visit 1 and is expected to remain stable for the duration of the trial.
- 6.1.9 Willing to allow the responsible authorities to be notified of participation in the trial, if mandated by local law.
- 6.1.10 Willing to allow his or her primary care practitioner (if he or she has one) and/or treating neurologist (if he or she has one) to be notified of participation in the trial, if the primary care practitioner/treating neurologist is different from the investigator.

Additional Inclusion Criteria at Randomization (Visit 2)

Patients are eligible for randomization in the trial if, in addition to continuing to meet the Screening (Visit 1) inclusion criteria, they also meet the following criterion prior to Visit 2 (Day 1):

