10.21 Adverse Events

10.21.1 Start and Stop Date Imputation

Table 10.21-1 Imputation Rules for Partial Adverse Events Start/Stop Dates

Parameter	Missing	Additional Conditions	Imputation
Start date for AEs	D	M and Y same as M and Y of first dose of study drug	Date of first dose of study drug
		M and/or Y not same as date of first dose of study drug	First day of month but should fall after 1st study drug intake or if impossible after informed consent date
	D and M	Y same as Y of first dose of study drug intake during period 1 and 2	Date of first dose of study drug
		Y after Y of first dose of study intake during Period 1 but same Y as 1 st study drug intake during Period 2	Date of first drug intake during period 2
		Y prior to Y of first dose of study drug but same as Y of informed consent date	Date of informed consent
		Y after Y of last study drug intake	The earliest date between date of last study drug intake + 14 days and end of study date
	D, M, Y	Not allowed by the system	Not applicable
Stop date for AEs	D	M and Y same as M and Y of last dose of study drug	The earliest date between date of last dose of study drug and end of study date
		M and/or Y not same as date of last dose of study drug	The earliest date between last day of month and end of study date
	D and M	Not allowed by the system	Not applicable
	D, M, Y	Not allowed by the system	Not applicable

AE = Adverse events; D = day; M = month; Y = year

Note: In all cases, if an estimated start date is after a complete stop date, use the first day of the stop date month.

Similarly, if the estimated stop date is before a complete or imputed start date, use the last day of the start date month.

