In order to flag prohibited medications taken in the study, each medication taken will be compared against a pre-specified list of all prohibited medications as presented in [Appendix 7](#), [Appendix 8](#) and [Appendix 9](#) along with their determination criteria.

All medications / non-drug therapies (e.g., physiotherapies) will be classified as follows:

- Prior medications are those the patient used prior to the first IMP intake. Prior medications can be discontinued before first administration or can be ongoing during the treatment periods (and wash-out period).
- Current medications are those the patient used at time of randomization and at the same time as study drug intake. This classification will mainly be used to summarize MS medications.
- Concomitant medications are any medications / non-drug therapies that are ongoing at the time of each study medication (e.g., nabiximols, placebo) intake; these medications can be initiated
 - Before first intake of study medication.
 - At the same time of study medication.

Medications concomitant the Period 1 study medication are those:

- Initiated before first intake of study medication,
- Initiated and /or taken at the same time of Period 1 study medication,
- Initiated and /or taken during the wash-out period.

Medications concomitant the Period 2 study medication are those:

- Initiated before first intake of Period 2 study medication,
- Initiated and /or taken at the same time of Period 2 study medication,

- Post treatment medications (FU medications) are any medications / non-drug therapies initiated following last IMP intake.

To classify each therapy in case of missing / partial start and /or stop date, imputation rules as described in [Section 10.14](#) will be applied.

All medications / non-drug therapies (including physiotherapies) taken during the trial will be summarized in the Safety Analysis Set. If it appears that the randomized treatment arm is different from the actual treatment arm (for summary by treatment arm) and/or if patients belonging to the Safety Analysis Set are different from those belonging to the FAS, medication summaries will be presented using both study populations.

The number and percentage of patients using each medication along with the number and percentage of patients using at least one medication within each medication group will be summarized. For each summary by treatment arm, a patient can be counted in both treatment arms for instance if:

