14	Study drug	Subject not exposed to IMP during at least 1 day during titration or the maintenance phase.
15	Study drug	Subject not exposed to IMP during at least 1 day in either treatment period.
16	Study drug	Patient receiving a kit number not allocated by IXRS which is not the treatment he/she was allocated to by IXRS during this period.
17	Efficacy endpoint	Missing evaluable MAS LLMT-6 pre-dose assessment.
18	Efficacy endpoint	Missing evaluable MAS LLMT-4 pre-dose assessment.
19	Efficacy endpoint	Missing evaluable MAS LLMT-6 at endpoint. (D21 or Day 51)
20	Efficacy endpoint	Missing evaluable MAS LLMT-4 at endpoint. (D21 or Day 51)
21	Visit window	Wash-out duration of less than 7 days.
22	Visit window	During maintenance phase: Visit 4 occurred +/- 2 days out of window

Number	Major IPD category	Major IPD criteria
		Visit 5 occurred +/- 3 days out of window Visit 6 occurred +/- 2 days out of window Visit 8 occurred +/- 2 days out of window Visit 9 occurred +/- 3 days out of window
23	Prohibited co-medication	Patient taking antipsychotic medication at any time during the trial.
24	Prohibited co-medication	Patient taking benzodiazepine on an as needed (PRN) basis during the trial.
25	Prohibited co-medication	Patient taking commercial cannabis or any cannabinoid medication during the trial.
26	Prohibited co-medication	Patient taking botulinum injection during the trial.
27	Prohibited co-medication	Initiation or changes in the dose of MS disease modifying therapy any time after randomization at Visit 2
28	Prohibited co-medication	Patient taking drugs solely metabolized by UGT1A9 and UGT2B7 during the trial
29	Prohibited co-medication	Patient taking strong CYP3A4 inducer during the trial
30	Prohibited co-medication	Initiation of a new course of physiotherapy any time after randomization at Visit 2
31	Prohibited co-medication	Patient changing dose or introducing antispasticity medication (baclofen, tizanidine, dantrolene)
32	Prohibited co-medication	Patient changing dose or introducing dalfampridine or fampridine

MS = Multiple sclerosis; MAS = Modified Ashworth Scale, IMP = Investigational Medicinal Product; IXRS = Interactive x Response System; LLMT-6 = Lower Limb Muscle Tone-6, LLMT-4 = Lower Limb Muscle Tone-6, PRN = pro re nata meaning as needed.

* Refers to important protocol which may or not be considered as major important deviation

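### SAP Table 10.14-1 dates partly recorded background drugs too late: a start known only to the first-dose month or year becomes Day 1, and the drug leaves the prior-medication tables

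*SAP*

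**What the plan says.** SAP Table 10.14-1 handles partial start dates as follows.

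- Day missing, "M and Y same as M and Y of first dose of study drug": the start is the first-dose date.
- Day missing, any other month or year: "First day of month but should fall on or after first study drug intake or if impossible after informed consent date".
- Day and month missing, "Y same as Y of first dose of study drug intake during Period 1 and 2": the start is the first-dose date.
- Day and month missing, year before the first-dose year: no row.
- Note to the table: "if an estimated start date is after a complete stop date, use the first day of the stop date month".

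The start rows are labelled as concomitant medications. However, section 10.14 covers prior and concomitant medication, and SAP 12.3.2 applies these rules to classify each therapy whose start or stop date is partial or missing. It also states that "Prior medications are those the patient used prior to the first IMP intake".

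Protocol 6.1.6 requires at least one oral antispasticity drug "that has been stable for at least 30 days prior to Visit 1". In SAP Appendix 1, failing that requirement is major deviation 03, and changing the dose of or introducing baclofen, tizanidine or dantrolene is major deviation 31. SAP 12.4 allows further major deviations to be found by programming on the blinded ADaM data.

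**The concern.** For adverse events a late imputed start is the cautious choice, because it counts a doubtful event as treatment-emergent. SAP Table 10.21-1 uses nearly the same floor for that purpose. For background medication the same floor works the wrong way: it takes a drug the patient was already on and records it as starting at or near the first dose. The SAP treats old dates differently elsewhere. In 10.12 a partial date of MS diagnosis or spasticity onset keeps its known month or year and is only capped at consent.

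At stake is whether the prior-medication tables describe correctly what patients were taking before the trial. A secondary possibility is that an imputed start is read as a protocol deviation.

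**Working it through.** The plan gives no figure to reproduce. The check applies the table to test records.

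**Assumed dates** (none are in the documents): consent, taken as Visit 1, 20 May 2021; first dose 10 June 2021; Period 2 first dose 10 July 2021, so both periods start in the same year. The drug is ongoing. A record is prior if the imputed start is before 10 June 2021.

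The row quoted in full above is ambiguous, so it is run three ways: (a) floor at first dose; (b) floor at consent, shown as the consent date itself (strictly, the day after); (c) recorded month kept where neither floor can be met within it.

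| Recorded start | (a) | (b) | (c) |
|---|---|---|---|
| June 2021 (first-dose month) | 10 Jun 2021, not prior | same | same |
| 2021 only (first-dose year) | 10 Jun 2021, not prior | same | same |
| May 2021 (consent month) | 10 Jun 2021, not prior | 20 May 2021, prior | 20 May 2021, prior |
| April 2021 | 10 Jun 2021, not prior | 20 May 2021, prior | 1 Apr 2021, prior |
| March 2015 | 10 Jun 2021, not prior | 20 May 2021, prior | 1 Mar 2015, prior |
| 2015 only, or 2020 only | no rule | no rule | no rule |

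**Rows 1 and 2** do not depend on the reading: the start is Day 1 and the drug is not prior.

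The qualifying antispasticity drug reaches this result through the year row. Under 6.1.6 it must have been stable from 20 April 2021 at the latest (30 days before 20 May). With year only recorded, a true start lies between 1 January and 20 April 2021. The imputed date is therefore late by at least 30 + 21 = 51 days (20 April to 20 May, then to 10 June) and at most 151 + 9 = 160 days (1 January to 1 June, then to 10 June).

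The first-dose-month row cannot catch that drug in an eligible patient. Thirty days before Visit 1, with Visit 1 at least one day before Day 1, is at least 31 days before first dose, which is always an earlier calendar month. That row affects other drugs begun earlier in the first-dose month.

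**April 2021 and March 2015** show the conflict in the remaining row. No day in either month is on or after first dose, or after consent. Enforcing a floor discards a known month, in the 2015 case by more than six years. Only reading (a) takes the drug out of the prior tables.

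**Year only, before the first-dose year**, gets no imputed date. The adverse-event table has a row for "Y prior to Y of first dose of study drug but same as Y of informed consent date", but that covers only the consent year and would not reach 2015 either.

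**The case against.** The strongest reply is that little follows from these dates, and most of it stands.

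- A reader might infer that every long-standing drug with an unknown month is redated into the trial. It is not. A year before the first-dose year has no row, and any date in such a year is prior anyway. This is a harmless gap.
- A reader might infer that an old drug with a known month always leaves the prior tables. It does so only under reading (a). That reading is hard to defend, since impossibility makes sense only relative to the recorded month. Under (b) and (c) the drug stays prior.
- A reader might infer that background medication is undercounted overall. SAP 12.2.5 describes baseline MS treatment by current medications, those taken at randomization or first dosing. A Day 1 start still counts there and in the concomitant tables.
- A reader might infer that patients will be wrongly removed from the per-protocol set. The SAP does not say that deviations use imputed dates. SAP 12.4 has the study team and sponsor review deviations, with the set fixed before lock, and major deviations only identify patients who may be excluded. Antispasticity use is also recorded in the diary for at least 7 days before Visit 2.
- Stopped drugs with a complete stop date before first dose are protected by the table note.

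The reply does not remove the two rows that give a Day 1 start under every reading, or the floor that cannot be met for a month before consent.

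**Conclusion.** The point holds as a minor error in a stated rule. Two rows of Table 10.14-1 give a start date that is wrong for any drug already in use at screening and take it out of the prior tables. A third row cannot be followed for months before consent without overriding recorded data.

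The effect is on the descriptive prior-medication tables. If, and only if, deviations are programmed from imputed starts, a Day 1 start for baclofen, tizanidine or dantrolene could resemble an introduction (deviation 31), and a start after consent could resemble a failure of the 30-day requirement (deviation 03). That could reach the per-protocol set and the count against the 20% exclusion threshold that triggers the per-protocol analyses (SAP 12.5.4.3.3).

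A reader should not infer any effect on the primary result. It uses the FAS, and the estimand in SAP Table 9.1-2 applies regardless of changes in other antispasticity medication.

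The number of records affected is unknown, because the documents give no share of partial dates. The 51 to 160 days rest on the assumed calendar.

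**What to change.** In Table 10.14-1:

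1. Apply the first-dose or consent floor only when it is compatible with the recorded month and year and the drug is not recorded as in use at screening.
2. Otherwise impute the first day of the recorded month, or 1 January of the recorded year, and add a row for years before the first dose.
3. Never impute a start after Visit 1 for a drug in use at screening. The Visit 1 concomitant-medication review should identify these; whether the eCRF carries a marker cannot be seen from the documents.

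In SAP 12.4 or Appendix 1, add one sentence: deviations 03 and 31 are derived from recorded, not imputed, start dates.

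The cost is a few table rows, one sentence and a small change to the medication derivation. No new data are needed. It is best done before database lock; after that, it would be described as a change from the SAP in the study report, as protocol section 13 provides.
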